2.4 Type of trial

This is a Phase 1, single-centre trial to assess the safety, tolerability, PK and food effect of BEN8744 in healthy volunteers.

This trial will be in 3 parts, as follows:

Part A will test single doses of BEN8744 in a double-blind, randomised, placebo-controlled and dose-escalating design.

Part B will test the effect of food on the PK of BEN8744 in an open-label, randomised, 2-way crossover design.

Part C will test repeated doses of BEN8744 (once or twice daily for 14 days) in a double-blind, randomised, placebo-controlled and dose-escalating design.

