8.1.2 Part B

Enrolment of up to 12 healthy subjects is planned, in up to 2 groups (Groups B1 and B2).

Each subject in Part B will have 2 study sessions (Sessions 1 and 2), in which they will receive a single dose of BEN8744, by mouth. Each subject will receive BEN8744 after an overnight fast of at least 10 h in one session, and after an FDA high-fat breakfast (1,013 kcal, 59.2 g fat [of which 28.1 g saturated fat]) in the other session; the order will be randomised 1:1, as shown in Table 7. A subject's doses

will be separated by a washout of at least 7 days (or 5 half-lives as determined in Part A, whichever is longer). Subjects dosed on the same day may be dosed at intervals of at least 10 min.

Table 7 Treatment sequence for each group (n=6 each) in Part B

	Session 1	Session 2
n=3 subjects	Fed	Fasted
n=3 subjects	Fasted	Fed

The dose to be tested in Group B1 will be decided following review of the interim safety, tolerability, and PK data from at least 3 dose levels in Part A, as described in section 8.5.3.

To reduce the risk of unexpectedly high plasma concentrations, the dose selected for Group B1 will be no higher than 50% of the highest dose tested in Part A that caused no safety concerns.

Group B2 is optional and may be required if the Sponsor decides to test the effect of food at an additional dose level (for example, if absorption and hence exposure is not proportional to dose in Part A) or under different conditions (eg with different fasting requirements or after a different meal such as a standard breakfast). The dose and food requirements for Group B2 will be decided following review of the interim safety, tolerability, and PK data from Group B1 and all available data from Part A.

Subjects will be screened within 28 days before their first dose of trial medication. Subjects will be resident on ward from 1 day before their dose (Day -1) until up to 72 h after dosing (Day 4). They will return for a follow-up visit 7 (± 2) days after their inpatient stay in Session 2 (Day 11 ± 2 days).

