10. Triplicate ECG recordings (made ≥ 2 min apart) will be made at screening; single recordings will be done at all other timepoints. Recordings should be made with subjects in a supine position, after resting for 5 min.
11. Pregnancy tests in women of child-bearing potential only. FSH tests in post-menopausal women at screening only.
12. The OAAS and VAS will be done immediately before PK blood samples frequently up to 72 h after dosing at the following timepoints: predose and postdose at 0.25, 0.5, 1, 2, 3, 4, 6 and 8 h; on Day 2 (24 h); and on Day 4 (72 h).
13. Blood samples for assay of BEN8744 will be taken on Day 1 at predose and postdose at 0.25, 0.5, 1, 2, 3, 4, 6, 8, 12 and 16 h; on Day 2 (24 and 36 h); on Day 3 (48 h); and on Day 4 (72 h) in each treatment session.
14. Continuous urine and faecal sample collection for exploratory characterisation of BEN8744 and its metabolites will be taken after dosing on Day 1 at 0–12 h, 12–24 h, 24–48 h, and 48–72 h.
A urine spot sample will be taken before dosing on Day 1.
A predose faecal sample will be collected from Day -2 to predose on Day 1 in Part B Session 1.

When more than one procedure is scheduled at a specific timepoint, procedures should be done in the following order: ECG, vital signs, blood samples (at the scheduled time). Blood sampling should be done on time. Other procedures should be done as close as possible to the scheduled timepoint.

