16.2.7 Pharmacokinetic data analyses

PK concentration data will be summarised using the PK concentration population. PK parameters will be summarised using the PK parameter population.

For log-transformed parameters, the primary measure of central tendency will be the geometric mean⁴¹; for untransformed parameters, it will be the arithmetic mean or median.

For all variables, N (number of subjects in receiving the treatment/formulation in the population), n (number of observations), arithmetic mean, median, minimum, maximum, SD, %CV (coefficient of variation), and the 95% CI of the arithmetic mean will be derived. For log-transformed variables, all of the above plus the geometric mean, its 95% CI, and the SD of the log-transformed variables, will be provided.

Plasma concentrations and PK parameters will be listed and summarised, by treatment, using descriptive statistics. Individual and mean plasma concentration–time profiles will be presented graphically. All available data will be used to derive PK parameters in individual subjects.

In Parts B and C, urine concentrations, and urine PK parameters will be listed and summarised, by treatment, using descriptive statistics.

Food effect analysis

To assess the effect of food in Part B, analysis of variance (ANOVA) models will be fitted with the logarithm of the PK parameters (AUC_{inf} , AUC_{last} and C_{max}) as the dependent variables, and formulation as a fixed effect. The estimated least square means and residual variance from the model will be used to construct 90% CIs for the difference in means on the log scale for the comparison of fed versus fasted solutions. Food effect will be concluded if the 90% CI of the ratio (fed:fasted) is not included within the range 80–125%.

For t_{max} , the Hodges Lehmann estimator of the difference between fed and fasted solutions in median values and the 90% CI generated with the Moses method will be presented.

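### Part B tmax: the plan names a two-sample (Moses) interval for fed and fasted values from the same subjects and states no step that uses the pairing

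*Combined protocol and SAP*

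**What the plan says.** Section 2.4 gives the design: "Part B will test the effect of food on the PK of BEN8744 in an open-label, randomised, 2-way crossover design". Section 8.1.2 makes the pairing explicit: "Each subject will receive BEN8744 after an overnight fast of at least 10 h in one session", with the dose taken after a high-fat breakfast in the other. Table 7 puts three subjects in each sequence of a group of six, and "the order will be randomised 1:1".

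Section 7.2.1 lists tmax among the primary PK endpoints of Part B. Section 16.2.7 gives it one fed-versus-fasted comparison: the "Hodges Lehmann estimator of the difference between fed and fasted solutions in median values and the 90% CI generated with the Moses method". That sentence does not say whether the method is applied to the raw fed and fasted values or to something derived within subject. It mentions no subject, period or sequence. The ANOVA for AUC and Cmax in the same subsection is described with the log parameter as the dependent variable "and formulation as a fixed effect", and names no other term.

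Part B blood samples are taken "predose and postdose at 0.25, 0.5, 1, 2, 3, 4, 6, 8, 12 and 16 h" on Day 1, with later samples up to 72 h (section 12.1.2). Section 16.2.1 says that a separate statistical analysis plan will be written before database lock.

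**The concern.** The Moses interval takes order statistics of all between-sample differences, with cut-offs from the rank-sum distribution. That distribution assumes two independent samples. Six fed and six fasted tmax values from the same six people are not independent, and a crossover is normally chosen because a person's two values are expected to be positively correlated. An unpaired interval discards that gain. Its cut-offs are too far out and it comes out too wide.

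What is at stake is how a food-related delay in absorption is described. The tmax comparison is an estimate with an interval and nothing else, so the interval is the result. If every subject is delayed by a similar amount but subjects differ among themselves, the unpaired interval can still reach zero. Correcting the ANOVA for AUC and Cmax would not change this, because tmax has its own named method.

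**Working it through.** **Inputs.** From the protocol: six subjects per group, three per sequence (Table 7); nominal level 90% (section 16.2.7); sampling times (section 12.1.2). Not in the documents, so assumed: the within-subject correlation ρ of tmax and, for the sampling-grid runs, a lognormal tmax with median 1.5 h and log-SD 0.43.

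**Nominal level if the samples were independent.** With 6 v 6 there are C(12,6) = 924 equally likely rank arrangements. P(U ≤ 7) = 43/924 = 0.0465. The interval from the 8th smallest to the 8th largest of the 36 fed-minus-fasted differences therefore has level 1 − 2 × 0.0465 = 90.7%. The stated 90% is reproduced, but only under independence.

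**Levels of the two within-subject alternatives (untied data).**
- Signed-rank, n = 6: P(W ≤ 2) = 3/64, so the 3rd smallest to 3rd largest of the 21 Walsh averages has level 1 − 6/64 = 90.6%. This also needs there to be no period effect.
- Moses on halved period differences, 3 v 3: C(6,3) = 20, so the smallest to largest of the 9 differences has level 1 − 2/20 = 90.0%.

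**Simulated behaviour with six pairs (20,000 to 40,000 runs).**

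| ρ (assumed) | Moses on raw values, coverage, untied normal | Width ratio Moses raw / signed-rank, untied normal | Width ratio on sampling grid | Signed-rank coverage on grid |
|---|---|---|---|---|
| 0 | 90.6% | 0.93 | 0.89 | 98.1% |
| 0.25 | about 94% | 1.07 | 1.00 | 98.7% |
| 0.50 | about 97% | 1.30 | 1.19 | 99.2% |
| 0.75 | about 99% | 1.8 | 1.6 | 99.7% |

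For untied normal data the signed-rank interval stays at about 90% to 91% at every ρ. At ρ = −0.3, Moses on raw values falls to 86.5%. On the grid, Moses on raw values covers 99.2% to 100%. With 12 pairs the pattern is the same (97.5% at ρ = 0.5).

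**Chance of showing a real delay.** For untied data with a 1 SD delay, the interval lies wholly above zero in 46% of runs with Moses on raw values against 65% with signed-rank at ρ = 0.50, and in 47% against 88% at ρ = 0.75. On the grid, for an assumed shift in median tmax from 1.5 h to 2.5 h at ρ = 0.50, the figures are roughly 40% for signed-rank and under 20% for Moses on raw values.

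**Hand example on the protocol's sampling times (hypothetical values).** Fasted 0.5, 1, 1, 2, 2, 3 h; fed 1, 2, 2, 3, 3, 4 h in the same order of subjects. Every subject is later when fed.
- Raw Moses: of the 36 differences, 5 are negative and 8 are zero, so the 8th smallest is 0. The largest are 3.5, 3, 3, 2.5, 2.5, then six values of 2, so the 8th largest is 2. Interval 0 to 2 h.
- Signed-rank: the within-subject differences are 0.5, 1, 1, 1, 1, 1. The Walsh averages are 0.5 (once), 0.75 (five times) and 1 (fifteen times). Interval 0.75 to 1 h.
- Moses on halved period differences: the 9 values are 0.75 (three times) and 1 (six times), whichever sequence holds the subject with 0.5. Interval 0.75 to 1 h.

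**Period effect.** With a 0.5 SD period effect and normal data, signed-rank coverage rises to about 93% to 94% at ρ = 0.50. With 1 SD it is 98.0% at ρ = 0.50 and 99.6% at 0.75. Moses on period differences stays at 89.9% to 90.1% with a 0.5 SD effect.

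**The case against.** The strongest reply is that the Moses method can be used correctly in a two-period crossover. Take each subject's period difference, halve it, and compare the two sequence groups, which are independent. The 3 v 3 allocation in Table 7 is the structure this needs, and its level is 90.0%. Section 16.2.7 does not exclude it. That stands. A reader might infer that the planned interval certainly has the wrong coverage, but the documents do not support this, because they do not say what the method is applied to. The sentence does, however, contrast fed with fasted rather than sequence with sequence, and the neighbouring ANOVA names only one effect. The unpaired reading is therefore the more natural one, and on the valid reading the text still needs the same one-sentence repair.

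Second, the untied-normal figures flatter the paired method. tmax is read from scheduled times, so ties are common and both intervals over-cover. This also stands: on the grid there is no width gain at ρ = 0.25 or below, and a signed-rank interval should not be described as having exact 90.6% coverage for tmax. A gain remains at moderate to high correlation.

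Third, the consequence is limited. There are no hypotheses (section 16.2.2), the 80–125% rule is stated for the fed:fasted ratio, the tmax interval is only presented, and individual PK parameters are listed, so a consistent delay would be visible there. All of this stands. It limits the weight of the point but does not justify labelling as 90% an interval built on the wrong sampling model.

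**Conclusion.** The point holds as a gap in specification whose natural reading gives the wrong interval. Section 16.2.7 names a two-sample method for paired tmax data and states no step that respects the pairing. Applied to raw values, the interval is a 90% interval only at zero within-subject correlation. At assumed correlations of 0.25 to 0.75 it covers about 94% to 99% for untied normal data and is 1.07 to 1.8 times as wide as the paired interval. On the sampling grid the ratio is about 1.0 to 1.6.

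These sizes rest on an assumed correlation, on normal data or the assumed lognormal tmax, and, for the grid, on nominal times. Section 16.1 uses actual times, which would turn many ties into near-ties.

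A reader might also infer that the plan risks declaring a spurious food effect on tmax. Under positive correlation the error runs the other way, towards missing a delay; under-coverage needs negative correlation. Nor would any formal food-effect conclusion change, since none is tied to tmax. The change is worth making because it is nearly free and tmax is a listed primary PK endpoint of Part B.

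**What to change.** Replace the tmax sentence in section 16.2.7, or at the least settle it in the statistical analysis plan that is still to be written, so that the analysis is within-subject. Either option resolves the point:

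- (a) Estimate the fed-minus-fasted difference in tmax by the Hodges-Lehmann (Walsh average) estimator of the within-subject differences, with a 90% CI from the Wilcoxon signed-rank distribution. State that the level is 90.6% at n = 6 for untied data with no period effect, and that the interval is conservative with tied tmax values.
- (b) Keep the Hodges-Lehmann estimate and Moses 90% CI, and state that they are applied to halved within-subject period differences compared between the two sequence groups. The level is 90.0% for 3 v 3 with untied data, and the interval is robust to a period effect. On the sampling grid it is also conservative, at about 96% for ρ = 0 and 97% for ρ = 0.5.

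Option (b) keeps the method already named and uses the randomised sequences. Option (a) is simpler and, for untied data with no period effect, slightly narrower (median width 1.60 against 1.65 SD at ρ = 0.5). The cost is one sentence and a few lines of code, with no extra subjects or samples.

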16.3 Determination of sample size

Since this is a Phase 1 study, no formal sample size determination is appropriate.

17 Ethical and regulatory requirements

The trial proposal will be reviewed by a recognised REC, and by the MHRA. The trial will not proceed unless the sponsor obtains from the MHRA a clinical trial authorisation (CTA), and the REC approves the trial.

The trial will be done at HMR, in compliance with The Medicines for Human Use (Clinical Trials) Regulations 2004 and current amendments⁴², The Medicines for Human Use (Clinical Trials) (Amendment) (EU Exit) Regulations 2019⁴³, The Human Medicines (Amendment etc) (EU Exit) Regulations of 2019 and 2020^{44,45}, GMP³⁷, the SOPs issued by RES for RECs in the UK³⁸, and Good Clinical Practice, which has its origins in the Declaration of Helsinki.

All subjects must give written consent to participate in this trial. Consent for screening evaluations may be obtained using the information and consent form for the HMR healthy volunteer panel, which has been approved by the Health Research Authority's Generic Review Committee. The trial-specific information and consent form will be signed by the subject either before any screening evaluation or after the investigator confirms the eligibility of the subject for the trial and before the subject is randomised to receive the first administration of IMP. Before giving consent, subjects must read the information sheet about the trial. They must also read the consent form. They will then discuss the trial with the investigator or his deputy and be given the opportunity to ask questions. The trial-specific information sheet and the consent form must be approved by the REC.

Each subject is free to withdraw from the trial at any time, without giving a reason. If a subject withdraws, the investigator will ask the subject to consent to a follow-up examination. For withdrawn subjects, the investigator will use a special information and consent form which has been ethically approved. If the subject consents to the

follow-up examination but asks the investigator to destroy all identifiable samples taken from the subject and/or not enter into the eCRF results of the follow-up examination, the investigator will comply with the subject's requests.

The sponsor will ensure that the MHRA and the REC, are informed promptly of SUSARs (see section 14.3), and that any new reports of SUSARs from other ongoing trials of the IMPs under investigation in this trial are notified to the MHRA, and to the REC, if applicable. The sponsor will provide the investigator, the REC and the MHRA with annual safety reports of each IMP under investigation, and listings of all suspected serious adverse reaction (SSAR) reports. The sponsor will also inform the investigator promptly of any new safety or toxicology data that might affect the safety of the subjects in this study.

The investigator will promptly inform the sponsor and, if applicable, the REC of any SAE that occurs during this trial (see section 14.3). The investigator will provide the REC with annual progress reports of the trial, if the trial lasts longer than a year.

The investigator will report to the REC any protocol deviation that is, in his opinion, of clinical significance. The investigator will also inform the REC in the event of several deviations which, although of no clinical significance, cause inconvenience and/or discomfort to the volunteers. The sponsor will notify the MHRA and REC of any serious breach of good clinical practice (for example, the investigator puts subjects' safety at risk, falsifies data, or persistently fails to comply with this protocol or good clinical practice).

Within 90 days after the end of the trial, the sponsor will ensure that the REC and the MHRA are notified that the trial has finished. If the trial is terminated prematurely, those reports will be made within 15 days after the end of the trial.

The sponsor will supply a summary of the clinical trial report to the MHRA and REC within 1 year after the end of the trial.

Trial procedures at HMR will be subject to audits by the HMR QA Department, to ensure compliance with the protocol and applicable regulatory requirements.

18 Trial documentation

18.1 Protocol amendments

After the protocol has been approved by the REC and the MHRA, no changes may be made without the agreement of both the investigator and the sponsor.

The MHRA and REC do not need to approve any substantial change to the protocol that needs to be implemented urgently to avoid an immediate hazard to trial subjects. The sponsor will ensure that the MHRA and REC are informed of urgent amendments or a temporary halt to the trial in accordance with The Medicines for Human Use (Clinical Trials) Regulations 2004 (and current amendments)⁴² and the SOPs issued by RES for NHS RECs³⁸.

All agreed protocol amendments will be recorded on a written agreement which will be signed and dated by the investigator and sponsor, and attached to the original protocol. The REC and/or MHRA must approve substantial amendments before they are implemented.

The standard text in our information and consent form template explains that the planned doses for Part A may change during the trial, and that we may give the subjects any dose that has been approved by the MHRA and REC in Part A. However, if we want to reduce the planned dose, we consider it essential to fully inform the subject of our reasons, because a reduction in dose might be due to poor tolerability, and that might affect the subject's decision to remain in the trial. Wherever possible, we will obtain prior approval from the REC for the information and consent form that we give to subjects before we reduce the dose. But, owing to the nature of trials on healthy volunteers, it is likely that we will sometimes have to implement an urgent amendment to lower the planned dose, to avoid immediate hazard to the subjects. We will fully inform the subjects of the reason for reducing the dose, and will notify the REC and MHRA promptly of the urgent amendment, in accordance with statutory requirements.

18.2 Case report forms

The eCRF will be designed and produced by HMR.

To preserve confidentiality, the CRF will not bear the subject's name. The subject number and/or HMR volunteer number will be used for identification.

The investigator is responsible for ensuring the accuracy and completeness of the data entered into the eCRF, and the timeliness of data entry. Clinical data (including AEs, concomitant medication, etc) will be entered into a 21 CFR Part 11-compliant Medrio database. The Medrio system includes password protection and internal quality checks, such as automatic range checks, to identify data that appear inconsistent, incomplete, or inaccurate. Data reported in the eCRF, derived from source documents, should be consistent with the source documents or the discrepancies should be explained. Where the data violate validation checks, queries will be generated for resolution by clinical staff. All edits made to the database upon resolution of queries will be recorded in an electronic audit trail.

Source documents

Before the start of the study, the sponsor and investigator will sign an agreement listing the source documents to be used in this trial.

18.3 Reporting of results

HMR will prepare a draft report for discussion with the sponsor. The report will contain results and discussion of the trial, to which will be attached tables, figures and listings in compliance with ICH E3⁴⁶.

Completed eCRFs will be supplied separately to the sponsor by HMR.

19 Obligations of the sponsor and investigator

19.1 Monitoring, auditing and inspection

The trial will be monitored by the sponsor.

A sample of documents generated by HMR which form part of this trial, and the ensuing data, will be audited by the HMR Quality Assurance Department to assess compliance with the quality management system of HMR. That system incorporates the requirements of The Medicines for Human Use (Clinical Trials) Regulations 2004 (and current amendments)⁴², ICH GCP, GMP³⁷, and the SOPs issued by RES for RECs in the UK³⁸, and is based on ISO 9001.

The sponsor may do a quality assurance audit, and regulatory authorities may inspect this study, at any time during or after the study. The sponsor and investigator agree to allow auditors and inspectors direct access to all relevant documents, and to allocate time to discuss findings with the auditors or inspectors.

